3.1.2.1. Operating Characteristics of the Stopping Rules for Futility

The futility stopping rule in Table 3 is based on the methodology of Lee et al. [Lee, 2008]. The optimal design has a maximum sample size of 28 and a type I error rate of 0.10 and power of 80.6%. The expansion cohort may be stopped early for futility if the predicted probability of success is less than 1.5%. Under the null hypothesis, if the true ORR is 40%, the expected sample size of the design is 20 subjects and probability of early termination is 86.1%. Under the alternative hypothesis, if the true ORR is 60%, the expected sample size is 28 and the probability of early termination is 15.6%.

Table 3 Decision Making Criteria for Futility Analysis

Number of Evaluable Subjects	\leq This Number of Responses to Stop Early for Futility	Probability of continuing enrolling when ORR=0.4	Probability of continuing enrolling when ORR=0.6
10	2	83.3%	98.8%
11	2	83.3%	98.8%
12	3	75.5%	98.1%
13	3	75.5%	98.1%
14	4	68.6%	97.5%
15	4	68.6%	97.5%
16	5	62.3%	96.9%
17	6	52.9%	95.7%
18	6	52.9%	95.7%
19	7	46.7%	94.9%
20	7	46.7%	94.9%
21	8	41.6%	94.2%
22	9	34.6%	92.8%
23	9	34.6%	92.8%
24	10	30.2%	91.9%
25	11	24.4%	90.2%
26	12	18.8%	87.7%
27	13	13.9%	84.5%
28	14	0.0%	0.0%

3.2. Primary and Final Analyses

The primary and final planned primary analyses will be performed after the completion of the following sequential steps:

1. All participants have completed the study as defined in the protocol.
2. All required database cleaning activities have been completed and final database lock (DBL) has been declared by Data Management.

Data from the two parts may be combined for some analyses at 15 months from LSFV and at the end of the trial, as appropriate.

4. ANALYSIS POPULATIONS

Population	Definition / Criteria	Analyses Evaluated
Screened	
 • All participants who were screened for eligibility 	
 • Study Population
Enrolled	
 • All participants who passed screening and entered the study. Included are: Run-in Failures; Randomized Participants; in non-randomized study and participants who were assigned a treatment in a non-randomised study. • Note screening failures (who never passed screening even if rescreened) and participants screened but never enrolled into the study (Reserve, Not Used) are excluded from the Enrolled population as they did not enter the study. 	
 • Study Population
All Treated	
 • All participants who received at least one dose of study treatment(s). 	
 • Efficacy, Safety, Study Population based on actual treatment received
COVID-19	
 • All participants in the All Treated population who had a confirmed, probable or suspected COVID-19 case diagnosis. 	
 • Baseline Characteristics, Medical History, Laboratory Data, and Safety
DLT Evaluable	
 • Participants fulfilling the 'All Treated' population criteria during part 1 (Dose Escalation) and are followed up for a 21-day period or withdrawn within 21 days due to an AE meeting the definition of a DLT as defined in Section 4.2.3.1 of protocol. 	
 • Summary of DLT for Part 1 only
All Evaluable	
 • It is considered when at least 10 subjects are evaluable if all the first 10 treated participants in the All Treated population meet at least one of the criteria below: 
 ○ if the planned assessment is every 3 weeks and at least three assessments are required, the time from the first dose to the time of data cut-off is more than 66 days, OR ○ had at least one disease assessment on or after day 60 OR ○ had an unconfirmed response of PR/CR or better, 	
 • Futility Analyses for the expansion cohort (for part 2 participants and part 1 participants who initially received the RP2D)

Population	Definition / Criteria	Analyses Evaluated
	OR 
 ○ progressed, OR ○ died, OR ○ discontinued treatment due to other reasons ● No skipping of participant is allowed, e.g., if the 11th treated participant does not meet one of the criteria above, the 12th treated participant will not be included even if one of the criteria is met for the 12th subject. 	
Pharmacokinetic (PK)	
 ● Participants in the All Treated population from whom at least one PK sample was obtained and analysed for belantamab mafodotin. 	
 ● PK
Pharmacodynamic (PD)	
 ● Participants in the All Treated population from whom at least one biomarker sample was obtained and analysed. 	
 ● PD/biomarker

Refer to [Appendix 11](#): List of Data Displays which details the population used for each display.

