2.2. Study Objective(s) and Endpoint(s)

Part 1: Dose Escalation

Objectives	Endpoints
Primary Objectives	Primary Endpoints

 To determine safety, tolerability and to establish the recommended Phase 2 dose (RP2D) of the combination of belantamab mafodotin and pembrolizumab in subjects with RRMM 	
 Percent of subjects with adverse events (AEs), changes in clinical signs and laboratory parameters Number of subjects with dose limiting toxicities (DLTs)
Secondary Objectives	Secondary Endpoints

 To evaluate clinical activity of the combination of belantamab mafodotin and pembrolizumab in subjects with RRMM 	
 Overall Response Rate (ORR), defined as the percentage of subjects with a confirmed partial response (PR) or better (i.e., PR, very good partial response [VGPR], complete response [CR] and stringent complete response [sCR]), according to the International Myeloma Working Group (IMWG) Response Criteria [Kumar, 2016].

 To evaluate the pharmacokinetic profile of belantamab mafodotin when administered intravenously in combination with pembrolizumab¹ 	
 Pharmacokinetic (PK) parameters following IV administration as data permit.

 To assess anti-drug antibodies (ADAs) against belantamab mafodotin¹ 	
 Incidence and titers of ADAs against belantamab mafodotin
Exploratory Objectives	Exploratory Endpoints

 To assess Minimal Residual Disease (MRD) in participants who achieve \geqVGPR or better 	
 Minimal Residual Disease (MRD) negativity rate, defined as: the percentage of subjects who are MRD negative in subjects who achieve VGPR or CR

 To characterize the relationship between clinical response and other biologic characteristics 	
 BCMA expression levels on malignant cells, serum sBCMA levels, serum cytokines, and immune cell characterization and their relationship to clinical response (Protein, RNA, DNA analysis)

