2.3. Study Design

Overview of Study Design and Key Features	
	
 Pembrolizumab
 
Dosing:
 
 -GSK2857916 and pembrolizumab -GSK2857916 first, Pembrolizumab second -If IRR related to GSK2857916, switch to pembrolizumab -Max treatment duration: 1 year
Design Features	
Population: Subjects with relapsed/refractory MM who have undergone stem cell transplant, or are considered transplant ineligible, and who have been previously treated with at least 3 prior lines that include the following: an IMiD (i.e. lenalidomide or pomalidomide), proteasome inhibitor (i.e. bortezomib, ixazomib or carfilzomib) and an anti-CD38 antibody alone or in combination.
 
 • Part 1 Dose Escalation (n = ~ 12 subjects) 
 ◦ Objective: characterize the safety, tolerability, PK, and immunogenicity of escalating doses of belantamab mafodotin in combination with 200 mg pembrolizumab to establish the RP2D. • Part 2 Expansion Cohort(s) (n=~28 subjects) 
 ◦ Objective: Further evaluate the safety, PK, immunogenicity, and clinical activity of belantamab mafodotin at the RP2 dose in combination with 200 mg pembrolizumab identified in Part 1 and to detect if meaningful overall response rate (ORR) can be achieved.
Dosing	
 • Part 1 Dose Escalation 
 ◦ Escalating doses of belantamab mafodotin (2.5 mg/kg, 3.4 mg/kg) will be administered first as an IV infusion once every three weeks (21 days = 1 cycle) in combination with the fixed dose of 200 mg pembrolizumab as an IV infusion to establish the RP2D. 
 ◦ Belantamab mafodotin will be administered first, as an IV infusion, followed by at least 1 hour rest. ◦ Provided there is no infusion related reaction (IRR) warranting a prolonged interval between dosing, pembrolizumab will be administered as second drug over approximately 30 min via IV infusion. • Part 2: Dose Expansion Phase 
 ◦ Subjects enrolled in Part 2 dose expansion phase will be administered belantamab mafodotin at recommended phase 2 dose (RP2D) established in combination with the fixed dose of 200 mg pembrolizumab based on Part 1 outcomes.
Time &	
 • Refer to Appendix 2: Schedule of Activities

Overview of Study Design and Key Features	
Events	

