
Treatment Cycle

 Actual Treatment Cycle will be derived based on cycle start date in exposure data to distinguish from assessment cycle.
Actual Treatment

 Subject's actual treatment will be derived from exposure data. If a subject's actual treatment is the same as assigned treatment, actual treatment is the assigned treatment; if a subject received treatment different from assigned treatment for the entire duration of treatment, actual treatment is different from assigned treatment. 
 Refer to the adjustments due to body weight in Section 6.4.1 of protocol. If time is not available for at least one of the study treatments, then GSK2857916 will be selected over pembrolizumab.
Time since Initial Diagnosis

 Calculated as the number of Days from the Date of Initial Diagnosis: 
 First Dose Date = Missing → Elapse Time = Missing Date of Initial Diagnosis = Completely/partially Missing → Elapse Time = Missing Otherwise → Elapse Time = First Dose Date – Date of Initial Diagnosis + 1

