16.6.4. Safety

Adverse Events
AE'S of Special Interest (belantamab mafodotin)

 Corneal events (GSK Scale): collected in eCRF Eye Disorders (CTCAE) Thrombocytopenia Infusion related reactions
AE'S of Special Interest (pembrolizumab)

 Overdose

Duration of AE

 Calculated as the number of days from AE Start Date to AE Stop Date: 
 AE Start Date = Missing → Elapse Time = Missing AE Stop Date = Missing → Elapse Time = Missing Otherwise → Elapsed Time = AE Stop Date – AE Start Date + 1
ECHO/MUGA

 Change from Baseline for cardiac data, e.g., Left Ventricular Ejection Fraction (LVEF), will be calculated based on the same modality (ECHO or MUGA) throughout the study for each subject. Post-baseline assessments with a different cardiac scan modality will not be used to calculate change from Baseline.

DLT
DLT Evaluable

 Participant is considered DLT evaluable if they fulfilled the 'All Treated' population criteria during part 1 (Dose Escalation) and are followed up for a 21-day period or withdrawn within 21 days due to an AE meeting the definition of a DLT as defined in Section 4.2.3.1 of protocol.

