16.7. Appendix 7: Reporting Standards for Missing Data

16.7.1. Premature Withdrawals

Element	Reporting Detail
General	
 Subject study completion (i.e. as specified in the protocol) was defined as: 
 For Part 1 and Part 2, a subject is considered to have completed the study if they received at least 1 cycle of combination study treatment, and: 
 The subject is followed until death, or The subject is followed until the end of study The end of study (defined as last subject's last visit) is defined as when all subjects have either died, progressed, withdrawn consent, or have been followed for a minimum of 24 months from the last subject first dose (LSFD). Following 24 months post LSFD, PACT will be implemented. At this time, the collection of data for all recruited participants who no longer receive study treatment will stop entirely and clinical trial database will be closed. Withdrawn subjects for other reasons other than toxicity, but prior to completion of DLT period will be replaced in the study for Part 1. All available data from participants who were withdrawn from the study will be listed and all available planned data will be included in summary Tables and Figures, unless otherwise specified. Withdrawal visits will be slotted as per Appendix 3: Assessment Windows or will be summarised as withdrawal visits.

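### DLT Evaluable turns on why a subject left, so a Part 1 subject with a DLT who leaves before Day 21 for another reason is missing from the only DLT summary table

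*SAP*

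**What the plan says.** SAP Section 4 builds DLT Evaluable on the All Treated population in Part 1 and adds one condition: subjects must be those who "are followed up for a 21-day period or withdrawn within 21 days due to an AE meeting the definition of a DLT". Section 16.6.4 repeats the rule as the derivation. Section 4 assigns the population to the Part 1 DLT summary only.

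Section 16.7.1 adds: "Withdrawn subjects for other reasons other than toxicity, but prior to completion of DLT period will be replaced in the study for Part 1". The footnote to Table 3.0089 (Section 16.11.7) says the same in the past tense. The programming note to that table defines the event by the protocol's criteria, clinical relevance, attribution and the 21-day window. The reason a subject later left plays no part in it.

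Section 2.2 lists the number of subjects with DLTs as a Part 1 primary endpoint. The objective it serves is to "establish the recommended Phase 2 dose (RP2D) of the combination of belantamab mafodotin and pembrolizumab in subjects with RRMM".

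On exposure, All Treated requires only one dose of study treatment. Section 16.6.2 handles the two drugs as separate study treatments: "If time is not available for at least one of the study treatments, then GSK2857916 will be selected over pembrolizumab". Section 2.3 gives belantamab mafodotin first and then: "Provided there is no infusion related reaction (IRR) warranting a prolonged interval between dosing, pembrolizumab will be administered as second drug".

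**The concern.** Whether a DLT occurred in the window is a fact about the subject. Under this definition, whether it is reported depends on something else: the recorded reason for leaving. A subject can have an event that meets every element of the DLT definition and still be outside the population in which DLTs are counted.

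A subject who leaves early without a DLT is uninformative and can reasonably be set aside. A subject who leaves early after a DLT has already supplied the outcome. The rule treats the two alike when the reason is not toxicity. What is at stake is the accuracy of a primary safety count in a very small group.

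A secondary point concerns exposure. Read literally, a subject given only one of the two drugs and followed for 21 days without a DLT is evaluable, although the objective is about the combination.

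**Working it through.** **1. Run the possible courses through the rule.** Route 1 is 21 days of follow-up. Route 2 is withdrawal within 21 days because of the DLT. The days in the third and last rows are illustrative.

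| Course in the window | Route 1 | Route 2 | DLT Evaluable | Replaced (Section 16.7.1) |
|---|---|---|---|---|
| DLT, followed to Day 21 | yes | – | yes | no |
| DLT, withdrawn because of it | no | yes | yes | no |
| DLT on Day 8, consent withdrawn Day 14 | no | no | **no** | **yes** |
| DLT, then withdrawn for toxicity that is not a DLT | no | no | **no** | not covered |
| No DLT, followed to Day 21 | yes | – | yes | no |
| No DLT, consent withdrawn Day 14 | no | no | no | yes |

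The third and last rows get the same treatment although only one of them carries an event. A subject who stops treatment after a DLT but stays in follow-up to Day 21 remains evaluable, so the gap is confined to rows three and four.

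**2. Size in the reported table.** The definition carries no figure of its own. Section 2.3 gives about 12 Part 1 subjects. Dropping one subject with a DLT gives:

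| Occurred | Reported, replacement has no DLT | Reported, no replacement |
|---|---|---|
| 1/3 = 33.3% | 0/3 = 0% | 0/2 = 0% |
| 2/3 = 66.7% | 1/3 = 33.3% | 1/2 = 50.0% |
| 2/6 = 33.3% | 1/6 = 16.7% | 1/5 = 20.0% |

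**3. Sensitivity of the mTPI table.** Section 3.1.1.1 gives a beta/binomial model with interval 25% to 35% centred on 30%. It does not state the prior or the exclusion cut-off. I assumed Beta(1,1) and exclusion when P(p > 0.30) > 0.95. The posterior is then Beta(1 + x, 1 + n − x), and the decision is the interval with the largest probability per unit length. All 27 cells of SAP Table 1 are reproduced. For 1/3, P(p > 0.30) = 0.7⁴ + 4 × 0.3 × 0.7³ = 0.240 + 0.412 = 0.652. For 0/3 it is 0.7⁴ = 0.240.

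If the evaluable set supplied the counts, and one DLT subject were dropped and replaced by a DLT-free one, Table 1 would read:

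- 1/3 (S) becomes 0/3 (E)
- 2/3 (D) becomes 1/3 (S)
- 3/3 (DU) becomes 2/3 (D)
- 2/6 (S) becomes 1/6 (E)
- 4/6 (DU) becomes 3/6 (S)
- 1/6 (E) and 3/6 (S) keep the same decision

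These shifts can be read straight from Table 1 without the assumed prior.

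**4. Direction of any rate bias.** Let p be the true DLT rate, q the share of DLT subjects lost early for another reason, and r the share of DLT-free subjects lost early. The expected rate among evaluable subjects is p(1 − q) / [p(1 − q) + (1 − p)(1 − r)]. The SAP gives neither q nor r, so these are assumed values, with p = 0.30:

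- r = 0; q = 10%, 25%, 50%: 0.27/0.97 = 27.8%; 0.225/0.925 = 24.3%; 0.15/0.85 = 17.6%
- q = r: the terms cancel and the rate is 30%
- q = 10%, r = 25%: 0.27/(0.27 + 0.525) = 34.0%

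The bias can therefore go either way, but in every case with q > 0 observed DLTs are left out of the count.

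**5. Exposure.** Section 16.7.1 shows that the SAP can require the combination: study completion needs subjects to have "received at least 1 cycle of combination study treatment". DLT Evaluable has no such condition.

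**The case against.** A reader might infer that the rule could have changed dose escalation or the recommended Phase 2 dose. The SAP does not support that. Section 4 limits the population to the DLT summary. Table 1 is indexed by patients treated at the current dose. Section 3.1.1.2 bases decisions on all available safety and tolerability data, and Section 3.1.1 puts the displays for the recommended dose in a separate plan. The SAP was first finalised on 27-OCT-2021, and Section 5.1 already labels Part 2 at 2.5 mg/kg, so it appears to postdate Part 1 dosing. This objection stands in full: the shifts in step 3 show sensitivity only.

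It can also be said that nothing is hidden. The event would appear in the All Treated adverse event tables and in Listing 1.0020, and Section 6.2 provides a listing of subjects excluded from each population. That is right, and it limits the harm. It does not repair the primary count, because Table 3.0089 is the only DLT table. Section 8.1 says DLTs will be listed, but Sections 16.11.14 and 16.11.15 contain no listing titled for them.

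On exposure, Section 2.3 describes an infusion reaction that lengthens the interval between the drugs. It does not say pembrolizumab is then omitted. A one-drug cycle is possible under the wording but is not shown to be expected, so this part stays secondary.

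Finally, death from myeloma before Day 21 is a tempting example of a replaced subject. It does not clearly fit: the rule concerns withdrawn subjects, and Section 16.7.1 treats follow-up until death as a route to completion.

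**Conclusion.** The point holds as a defect in a reporting population. On the SAP's own wording, a subject with a DLT who leaves follow-up before Day 21 for a reason other than that DLT is omitted from the only summary table for a Part 1 primary endpoint. If the reason was not toxicity, the subject is also treated as replaced. No other section corrects this.

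The size is one subject at a time among about 12, enough to move a cohort's reported rate from 33.3% to 0%. Nothing in the SAP shows that any subject was affected. A reader might infer that the rule always lowers the DLT rate. It does so in expectation only if subjects with a DLT leave early more often than those without. With equal departure the expected rate is unchanged, although an observed event is still lost.

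The protocol is not shown. In its DLT Evaluable definition the SAP cites the protocol only for what a DLT is, so evaluability is fixed here. Importance: moderate.

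**What to change.** In Sections 4 and 16.6.4, define DLT Evaluable as All Treated Part 1 subjects who either had a DLT at any time in the 21-day window, whatever the later reason for leaving, or completed 21 days of follow-up without a DLT.

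Align the Table 3.0089 footnote with that definition. Reconcile the Section 16.7.1 replacement wording with the protocol, since replacement is trial conduct and cannot be changed by the SAP alone. List any subject whose status differs between the two definitions.

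In Table 3.0089, flag any DLT-free subject who did not receive both drugs in Cycle 1, or show the table with and without them.

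The cost is wording, one population flag and one table note. There is also a statistical cost. Early leavers with a DLT are counted while early leavers without one are not, so in the notation of step 4 the expected rate becomes p / [p + (1 − p)(1 − r)]. At p = 0.30 and r = 10% that is 0.30/0.93 = 32.3%. This errs on the cautious side for a safety endpoint and keeps every observed DLT in the count.

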3.1.2. Part 2 Dose Expansion Phase

Continuous safety monitoring will be conducted for the expansion cohort starting from when 5 subjects are dosed. The observed number of treatment-related Grade 4 or higher AEs will be compared against the safety stopping rule in [Table 2](#). Enrollment may stop if the safety stopping rule is met based on totality of safety data. For example, if there are 3 events out of 5 dosed subjects, enrollment may stop after review of all safety data; if there is 2 or fewer events out of 5 dosed subjects, enrollment will continue. Operating characteristics for the safety stopping rule are provided in [Figure 1](#). The iSRC will review and may implement Part 2 safety stopping rules, if pre-specified criteria are met. Details of the planned analyses for the iSRC data review meetings, including subject demographic, subject disposition, AE and SAE data, are documented in a separate RAP.

Table 2 Safety Stopping Rules for the Expansion Cohort

Number of dosed subjects	Stop if treatment related Grade 4 or higher AEs larger or equal to this this number
5	3
6-10	4
11-14	5
15-19	6
20-25	7
26-28	8

Figure 1 Operating Characteristics of Safety Stopping Rule for Expansion Cohort

Interim analyses for ORR will start when at least 10 subjects are evaluable as defined in Section 4. Subjects who initially received RP2D in Part 1 may also be included. The observed number of subjects with unconfirmed response of PR or better will be compared with the stopping boundary in Table 3. Enrolment may stop if the stopping rule is met. Final decision will be based on the totality of data. For example, if there are 2 unconfirmed responses out of 10 evaluable subjects, enrolment may stop after review of all available data; if there are 3 or more unconfirmed responses out of 10 evaluable subjects, enrolment will continue. More details of the operating characteristics for futility analysis are provided in Section 3.1.2.1.

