7.2.1.3. Population of Interest

At futility interim, the primary efficacy analysis of ORR will be based on the All Evaluable population.

Otherwise, the primary efficacy analysis of ORR will be based on the All Treated population, unless otherwise specified.

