8. SAFETY ANALYSES

The safety analyses will be based on the All Treated population, unless otherwise specified.

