3.008	All Evaluable	AE13	Adverse Event Overview	
Report for: futility interim analyses for part 2 participants and part 1 participants who initially received the RP2D (Refer to Section 5.1 for ordering of dose level)
 
Add the following footnote: A subject is evaluable for interim analysis if the subject fulfils the criteria for 'All Treated' population with adequate baseline assessment and measurable disease meet at least one of the following criteria: if the planned assessment is every 3 weeks and at least three assessments are required, the time from the first dose to the time of data cut-off is more than 66 days, OR had an unconfirmed response of PR/CR or better, progressed, OR died, OR discontinued treatment due to other reasons
	IA [1]
3.009	All Treated	AE3	Summary of All Adverse Events by Preferred Term	
Report for: Part 1, Part 2, and combined Part 1 and Part 2; Summarize by: dose level (Refer to Section 5.1 for ordering of dose level and omit 1.92 mg/kg if data is not available) Total.
	P-SAC [3], F-SAC [4]

Safety: Tables					
No.	Population	IDSL / Example Shell	Title	Programming Notes	Deliverable [Priority]
3.0010	All Treated	AE3	Summary of Common (>=5%) Grade 2-4 Adverse Events by Overall Frequency	Report for: Part 1, Part 2, and combined Part 1 and Part 2; Summarize by: dose level (Refer to Section 5.1 for ordering of dose level and omit 1.92 mg/kg if data is not available) Total.	P-SAC [3], F-SAC [4]
3.0011	All Treated	AE5B	Summary All Drug-Related Adverse Events by System Organ Class and Preferred Term and Maximum Grade	Report for: Part 1, Part 2, and combined Part 1 and Part 2; Summarize by: dose level (Refer to Section 5.1 for ordering of dose level and omit 1.92 mg/kg if data is not available) Total.	P-SAC [3], F-SAC [4]
3.0012	All Treated	AE15	Summary of Common (>=5%) Non-serious Adverse Events by System Organ Class and Preferred Term (Number of Subjects and Occurrences)	Report for: Part 1, Part 2, and combined Part 1 and Part 2; ; Summarize by: dose level (Refer to Section 5.1 for ordering of dose level and omit 1.92 mg/kg if data is not available) Total..	P-SAC [3], F-SAC [4]
3.0013	All Treated	AE3	Summary of Common (>=5%) Drug-Related Grade 2-4 Adverse Events by Overall Frequency	Report for: Part 1, Part 2, and combined Part 1 and Part 2; Summarize by: dose level (Refer to Section 5.1 for ordering of dose level and omit 1.92 mg/kg if data is not available) Total.	P-SAC [3], F-SAC [4]

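### The exposure, safety and dose-modification tables for the futility interim use the All Evaluable population, which is built for the response count, so they can leave out dosed subjects and their events

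*SAP*

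**What the plan says.** **Population.** SAP Section 4 makes a treated subject evaluable on any one of several criteria:
- with three-weekly assessments, "the time from the first dose to the time of data cut-off is more than 66 days";
- a disease assessment on or after day 60;
- an unconfirmed response;
- progression;
- death;
- discontinuation of treatment for other reasons.

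Inclusion follows the order of treatment and stops at the first subject who meets none of these. If that is the 11th, "the 12th treated participant will not be included even if one of the criteria is met for the 12th subject".

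**Purpose.** Section 4 lists futility analyses as the use of All Evaluable, and names All Treated for efficacy, safety and study population. Section 7.2.1.3 states: "At futility interim, the primary efficacy analysis of ORR will be based on the All Evaluable population". Section 8 states: "The safety analyses will be based on the All Treated population, unless otherwise specified".

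**Displays.** In Appendix 11 every table with deliverable IA [1] is on All Evaluable. Nine of them concern exposure, safety or dose modification:
- 1.0022, exposure;
- 3.008, adverse event overview;
- 3.0025, eye disorders;
- 3.0027, thrombocytopenia;
- 3.0080, dose reductions;
- 3.0082 and 3.0084, dose delays of each drug;
- 3.0086 and 3.0088, infusion interruptions of each drug.

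The programming note for 3.008 is typical: "Report for: futility interim analyses for part 2 participants and part 1 participants who initially received the RP2D".

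**Separate safety rule.** Section 3.1.2 adds: "Continuous safety monitoring will be conducted for the expansion cohort starting from when 5 subjects are dosed". Its Table 2 is indexed by the number of dosed subjects. The iSRC reviews it, with displays in a separate RAP. On futility, the same section says: "Final decision will be based on the totality of data".

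**The concern.** The evaluability and no-skipping rules protect a response rate. They stop early responders from being counted ahead of slower subjects treated before them. Neither purpose applies to adverse events, exposure or dose changes, which count from the first dose. Applied to those tables, the rules only remove data already in the database, and the denominator becomes smaller than the number exposed.

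The footnotes make this hard for a reader to see. Both versions list death and discontinuation as making a subject evaluable, and neither mentions no-skipping, so a reader would take all such subjects to be counted. The versions also differ from Section 4 and from each other:
- The one on 1.0022, 3.008, 3.0025 and 3.0027 adds adequate baseline assessment and measurable disease, and omits the day-60 criterion.
- The one on 3.0080 to 3.0088 includes day 60, but turns the 66-day criterion into 66 days plus at least three assessments actually done.

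At stake is whether those reading the planned interim tables see the safety experience of everyone dosed at the RP2D by the cut-off.

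**Working it through.** **1. The plan's own safety denominator.** Section 2.4.2 gives a 12% reference rate and one-sided alpha of 0.025. For each number dosed n, I took the smallest r with P(X ≥ r | n, 0.12) ≤ 0.025 (exact binomial).

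| n | Table 2 boundary r | P(X ≥ r) | P(X ≥ r − 1) |
|---|---|---|---|
| 5 | 3 | 0.0143 | 0.1125 |
| 10 | 4 | 0.0239 | 0.1087 |
| 25 | 7 | 0.0243 | 0.0709 |
| 28 | 8 | 0.0145 | 0.0435 |

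Table 2 reproduces at all 24 values of n from 5 to 28. It works on dosed subjects, so the evaluability and no-skipping rules do not touch it.

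**2. What no-skipping does to a safety table (hypothetical case).** Subjects 1 to 10 are evaluable. Subject 11 was dosed 40 days ago, has no response and is still on treatment. Subject 12 was dosed 30 days ago and has died. Death is a criterion, but subject 11 closes the list, so All Evaluable stays at 10. The nine tables show 10 subjects and omit that death, although 12 were dosed.

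**3. How many could be absent at the first look.** The documents give no accrual rate, so this is an assumption: uniform accrual of 1 to 4 per month. The 10th subject becomes evaluable only by the 66-day criterion, which puts the cut-off on day 67 after that subject's first dose. No later subject is evaluable.

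- Interval between subjects: g = 30.4 / rate days.
- Subjects dosed after the 10th by the cut-off: k = 67 / g, rounded down.
- Share absent: k / (10 + k).
- Chance that the absent subjects include at least one treatment-related Grade 4 or higher event at the 12% rate: 1 − 0.88^k.

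| Rate per month | g (days) | 67 / g | k absent | Dosed | Share absent | 1 − 0.88^k |
|---|---|---|---|---|---|---|
| 1 | 30.4 | 2.2 | 2 | 12 | 17% | 23% |
| 2 | 15.2 | 4.4 | 4 | 14 | 29% | 40% |
| 3 | 10.1 | 6.6 | 6 | 16 | 38% | 54% |
| 4 | 7.6 | 8.8 | 8 | 18 | 44% | 64% |

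The last column shows how readily a relevant event could fall outside these tables. It is not the chance that such an event goes unseen, because the rule in step 1 counts it.

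**4. Effect of a change of population.** Recomputing Table 3 from its boundaries gives the stated continuation probabilities for n = 10 to 27, with a type I error of 0.0997 and power of 80.6%. These depend on the response count only. Moving the nine tables to All Treated changes neither Table 2 nor Table 3.

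**The case against.** A reader might infer that enrolment continues on tables blind to deaths and toxicities in recent subjects. The document does not support that. A treatment-related Grade 4 or higher event, including a fatal one, counts against Table 2 from the fifth dosed subject, whatever the subject's evaluability. The iSRC sees adverse event and serious adverse event data under a RAP that is not at hand, so no gap in its review can be asserted. Section 3.1.2 ties a futility stop to review of all available data. Appendix 11 schedules no interim table of deaths (3.0058), serious adverse events (3.0043, 3.0045) or GSK-scale corneal events (3.0023), so the interim set reads as context for the response count and not as the safety package.

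Nor is there a formal contradiction. The Section 8 default allows exceptions, and Appendix 11 makes them. Showing toxicity on the same subjects as response, with comparable follow-up, is a recognisable choice: Section 8.2.1.1 bins onset of eye disorders and thrombocytopenia out to 43–63 and beyond 63 days, and recently dosed subjects would dilute those percentages.

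The size is also soft. Response, progression, death, discontinuation or a day-60 assessment can make a subject evaluable sooner, and earlier-treated Part 1 subjects at the RP2D may count among the first ten. Finally, the latest SAP amendment concerns final-analysis displays, and Appendix 11 footnotes subjects going on to PACT, so enrolment appears complete and the looks past.

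Most of this stands against the consequence. It does not justify the population. The plan gives no reason for the exception, and a matched view could be an extra column. The iSRC boundary covers one class of event. The iSRC displays, as this SAP describes them, do not name exposure, dose modifications, or the eye-disorder and thrombocytopenia summaries. For those, the restricted version is the only interim one planned here.

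**Conclusion.** All nine tables are on a response-readiness population, and its no-skipping rule can drop later-treated subjects who have died or stopped treatment, without a footnote saying so. The planned interim tables are therefore incomplete for safety. This is a weakness of display that is cheap to correct. It is not a design failure, and it does not show that safety data were missing from the enrolment decision.

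The range of 2 to 8 absent subjects out of 12 to 18 dosed (17% to 44%) rests wholly on the assumed accrual of 1 to 4 per month, the full 66-day lag for the 10th subject, and no later subject being evaluable. Earlier evaluability would shrink it and faster accrual would enlarge it. The population assignments and the missing no-skipping footnote can be read directly from the SAP and need no assumption.

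**What to change.** - In Appendix 11, put Tables 1.0022, 3.008, 3.0025, 3.0027, 3.0080, 3.0082, 3.0084, 3.0086 and 3.0088 on All Treated subjects at the RP2D (Part 2 plus Part 1 subjects who initially received it) up to the data cut-off. Add an All Evaluable column if a view matched to the response count is wanted.
- Keep All Evaluable for Table 2.002 and Listing 1.0055.
- Bring the evaluability footnotes into line with Section 4, including the day-60 criterion, and state the no-skipping rule wherever All Evaluable is shown.
- Cross-refer from the interim displays to the iSRC outputs.
- If the looks have already been made, record for each the number dosed at the RP2D beside the number evaluable, and any deaths or discontinuations outside All Evaluable.

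**Cost.** A population column and footnotes in nine shells. No new data are needed, and Tables 2 and 3 do not change. The downside is that the added subjects have short follow-up, which dilutes crude percentages. A footnote should say so.
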